3.6.3 Vital Signs

Vital signs parameters (weight, body mass index, blood pressure [systolic and diastolic blood pressure], heart rate, body temperature, and respiration rate) will be summarized using descriptive statistics for by visit for each treatment group. The changes from baseline will also be presented.

A listing of all vital signs will be provided by subject.

3.6.4 Electrocardiograms

Electrocardiogram (ECG) parameters (PR, QRS, QT, and RR) will be summarized using descriptive statistics at baseline and Week 6/Early Termination for the treatment group. The overall interpretation will be summarized by counts and percentages by treatment group and total.

All ECG measurements and the overall interpretation will be listed by subject.

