2.2 Study Design

2.2.1 *Overview*

[figure not shown]
This study will be conducted at approximately 20-25 sites in the United States. The Phase 2 study of levosimendan in PH-HFpEF subjects has been designed in two phases (Figure 1). The study will recruit male and female subjects meeting identified enrollment criteria for PH-HFpEF into the lead-in open label phase to identify “responders” to levosimendan intravenous infusion of at 0.10 µg/kg/min for 24 hours \pm 30 min. Subjects that have clinically relevant responses to levosimendan will be randomized to levosimendan or placebo (1:1) and receive intermittent (weekly) study drug infusions (Week 2-5). The first 36 subjects who demonstrate a \geq 4mmHg reduction in PCWP from baseline measured at bicycle exercise (25 watts) with no more than a 10% decrease from baseline in cardiac index will be classified as a “responder” to the

lead-in levosimendan dose and be randomized to the double-blind phase of the study. Patients who do not tolerate the initial levosimendan infusion due to excessive hypotension or tachycardia will be dropped from eligibility. In the double-blinded phase, patients will be randomized to levosimendan or placebo and receive a weekly dose of study drug intravenously at $0.075 \mu\text{g}/\text{kg}/\text{min}$ for 24 hours ± 30 min and if tolerated titrated to $0.10 \mu\text{g}/\text{kg}/\text{min}$ for 24 hours ± 30 min at Week 4. The infusion rate of study drug may be decreased or interrupted as clinically warranted if the subject has hypotension, tachycardia, or signs or symptoms consistent with hypovolemia (e.g., low systolic blood pressure [SBP], decreasing urine output with rising blood urea nitrogen [BUN] and serum creatinine) Record the time of discontinuation or down titration. Patients should be monitored closely until clinically stable. See Protocol Attachment 1 for infusion rates and instructions on dose adjustments. Patients will be evaluated Week 6 to determine the efficacy and safety of levosimendan. Randomized subjects that have not received study drug weekly through Week 5 and returned for evaluation on Week 6 will be replaced to ensure 18 subjects have completed in each study group.

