3.6.1 Adverse Events

An AE is any untoward medical occurrence in a clinical investigation subject administered a pharmaceutical product and that does not necessarily have a causal relationship with this treatment. All AEs are collected from the time the informed consent is signed until the subject discontinues or until Week 6 (whichever is first). All AEs will be coded to system organ class and preferred term using MedDRA version 21.0. Treatment-emergent adverse events (TEAEs) are defined as AEs that start after the first dose of study drug (lead-in infusion).

TEAEs with onset during the lead-in phase and double-blind phase will be summarized separately. TEAEs that start on or after the lead-in infusion and prior to the first double-blind infusion will be attributed to the lead-in phase, while TEAEs that start on or after the first double-blind infusion will be attributed to the double-blind phase. All AEs that start prior to the lead-in infusion will be listed.

Adverse events of special interest include the following preferred terms: hypotension, atrial fibrillation, clinically significant arrhythmia, aborted resuscitated death, and stroke.

An overview of TEAEs will be provided including counts and percentages of subjects with the following:

- Any TEAEs (overall and by maximum severity)
- Any study drug related TEAEs (overall and by maximum severity)
- Any TEAEs of special interest (overall and by maximum severity)
- Any serious TEAEs (TESAEs)
- Any TEAEs leading to discontinuation of study drug
- Any TEAEs leading to discontinuation of study
- Any TEAEs leading to death

Counts and percentages of subjects will also be presented by system organ class and preferred term for each of the categories in the overview.

Listings will be presented specifically for SAEs and TEAEs leading to discontinuation of study drug.

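### The ECG summary reports QT and RR separately with no rate-corrected QT, so a heart-rate difference at the time of the ECG could hide or exaggerate a repolarisation effect

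*SAP*

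**What the plan says.** Section 3.6.4 of the SAP names four intervals: "Electrocardiogram (ECG) parameters (PR, QRS, QT, and RR) will be summarized using descriptive statistics". They are "summarized using descriptive statistics at baseline and Week 6/Early Termination for the treatment group". The section adds counts and percentages for the overall interpretation, and a listing: "All ECG measurements and the overall interpretation will be listed by subject". It mentions no QTc, and neither does the rest of the SAP. Section 5, which records departures from the protocol, does not mention the ECG.

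Three other places bear on the point:

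- **Heart rate on drug.** Section 2.2.1 says of the lead-in: "Patients who do not tolerate the initial levosimendan infusion due to excessive hypotension or tachycardia will be dropped from eligibility". For study drug it allows the infusion rate to be reduced or interrupted "as clinically warranted if the subject has hypotension, tachycardia, or signs or symptoms consistent with hypovolemia".
- **Rhythm as a safety concern.** Section 3.6.1 lists the events of special interest as "hypotension, atrial fibrillation, clinically significant arrhythmia, aborted resuscitated death, and stroke".
- **Heart rate elsewhere.** Section 3.6.3 summarises heart rate by visit and arm, with change from baseline. It does not link it to QT.

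**The concern.** The QT interval depends on heart rate, so raw QT values recorded at different rates are not comparable. A drug that lengthens repolarisation and also raises heart rate can leave raw QT unchanged. If heart rate falls between visits, raw QT lengthens with no repolarisation effect at all.

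The SAP fixes its list of ECG intervals and leaves out the one derived quantity that addresses this, although both ingredients are in the list. What is at stake is how readable one safety table is in a trial whose own plan treats arrhythmia as being of special interest. If QTc is needed later, its formula would be chosen after the data are known.

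**Working it through.** The SAP states no QT, QTc or heart-rate figure, so there is nothing of its own to reproduce. The check has two parts.

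**1. When are the ECGs taken, relative to dosing?**

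- From section 3.1.3, the Week 5 visit is nominally Day 29 and Week 6 is Day 36. 36 − 29 = 7 days after the last scheduled infusion. The SAP does not say that heart rate is still raised then, or that it differs between arms.
- The time point in section 3.6.4 also includes Early Termination. Under section 2.2.1, subjects who stop early have the Week 6 procedures as soon as possible. Right heart catheterisation, echocardiogram and walk test are waived; the ECG is not among the waived items. The rule on the 24-hour phone call allows for stopping within 24 hours of an infusion.
- Section 3.6 bases safety summaries on the Safety Analysis Set, so early terminators are in this table.

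Some ECGs can therefore fall close to dosing, possibly in subjects who stopped because of tachycardia. Most should not.

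**2. How large is the rate effect?**

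Inputs (all assumptions): QTcF constant at 420 ms, starting heart rate 70 bpm, rises of 0 to 20 bpm. RR in seconds = 60/HR. Fridericia: QTcF = QT / RR^(1/3), so QT = QTcF × (60/HR)^(1/3).

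| HR (bpm) | Raw QT (ms) | Change from 70 bpm (ms) |
|---|---|---|
| 70 | 420 × (60/70)^(1/3) = 399.0 | 0 |
| 75 | 420 × (60/75)^(1/3) = 389.9 | −9.1 |
| 80 | 420 × (60/80)^(1/3) = 381.6 | −17.4 |
| 90 | 420 × (60/90)^(1/3) = 366.9 | −32.1 |

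Read from 80 down to 70 bpm, the same figures show raw QT lengthening by 17.4 ms with no repolarisation effect.

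The reverse view gives similar sizes. Assume raw QT is 400 ms at both visits, so that the planned summary shows no change. From 70 bpm, a rise of 5, 10 or 20 bpm then corresponds to a QTcF increase of 9.8, 19.2 or 36.8 ms. For a 10 bpm rise the increase is 21.1 ms starting from 60 bpm and 17.6 ms starting from 80 bpm.

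**Choice of formula.** For the same unchanged QT of 400 ms and a rise from 70 to 80 bpm, Fridericia gives 19.2 ms. Bazett, QT / RR^(1/2), gives 400/(60/80)^(1/2) − 400/(60/70)^(1/2) = 461.9 − 432.0 = 29.8 ms (from unrounded values). A formula chosen after unblinding would leave that difference open.

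**The case against.** The strongest reply is about timing. The SAP names tachycardia as a tolerability matter around the infusion, while the main ECG time point is about a week later. If heart rate is back at baseline by then, the effect is the first row of the table: zero. Nothing in the SAP contradicts this, and it stands for most subjects. It does not cover Early Termination ECGs.

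The second reply is that the information is largely there. RR is summarised beside QT, heart rate is summarised by visit, every ECG measurement is listed, and the overall interpretation is tabulated. Rhythm is also covered by cardiac monitoring shifts to Week 5 (section 3.6.5) and by the events of special interest. A careful reader can even approximate mean QTcF from mean QT and mean RR. In one simulated sample of 18 under assumed values, the mean of the individual QTcF values was 420.1 ms and the value from the two means was 419.8 ms. So a shift in a group mean need not go unnoticed. What separate summaries of QT and RR do not give is each subject's QTc, its spread, or its change from baseline. Section 3.6.4 states no change from baseline for any ECG interval, unlike sections 3.6.2 and 3.6.3 for laboratory values and vital signs.

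Third, the protocol is not at hand, and the programming specifications are a separate document (section 6); either might define QTc. That is possible, but the SAP itself sets the list of summarised intervals, and QTc is not on it.

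A reader might infer that the plan expects tachycardia in the levosimendan arm and that its ECG table will therefore be falsely reassuring. The SAP does not support that. It foresees tachycardia as a reason to change or stop an infusion, gives no incidence or size, and rests no test, threshold or safety conclusion on QT.

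**Conclusion.** The point holds as a minor weakness in safety reporting. The planned QT summary is open to confounding by heart rate, and the SAP plans no rate-corrected measure although it collects what is needed to derive one. Masking or exaggeration is possible, not shown. It requires a heart-rate difference between visits or arms when the ECG is taken, which is most plausible at Early Termination close to dosing and less so at Week 6.

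The size is roughly 9 ms for a 5 bpm rise, 17 ms for 10 bpm and 32 ms for 20 bpm, and nil if heart rate is unchanged. These figures rest on an assumed QTcF of 420 ms, a 70 bpm start and the Fridericia relation, not on trial data. The efficacy analyses are not affected. Nor does the point show that raw QT should be dropped: it is a legitimate entry in the table once QTc stands beside it.

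**What to change.** In section 3.6.4, define QTcF = QT / RR^(1/3), with RR in seconds, for each subject and ECG. Summarise its values and its change from baseline by treatment group, in addition to QT and RR, and add it to the listing. Name the formula before unblinding.

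The cost is one derived variable and a few table rows, with no new data or visits. The small downside is that correction by a single RR is less reliable in subjects with atrial fibrillation. Flag those subjects in the table so that their values can be read with care.

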3.6.5 Cardiac Monitoring

Selected cardiac monitoring parameters will be summarized using descriptive statistics at baseline and Week 5 for the treatment group. Shifts from baseline to Week 5 will be presented for the clinical alert findings by treatment group and total.

All Cardiac monitoring data will be listed by subject.

3.6.6 Other Safety Parameters

The pregnancy test and Child-Pugh classification will be listed by subject and visit.

4 INTERIM ANALYSIS

No interim analysis is planned for this study.

5 CHANGES FROM PROTOCOL-SPECIFIED STATISTICAL ANALYSES

The protocol states that the hemodynamic variables will be analyzed using an ANCOVA model with effects for treatment and investigative site. The model name is corrected to be ANOVA model in the SAP.

The protocol states that one of the secondary endpoints is “Exercise duration 6-min walk test at Week 6”. To clarify the endpoint, this endpoint is updated to “6MWT at Week 6 (distance)” in the SAP.

The change in mPAP and RAP (at rest and with exercise, baseline vs Week 6) are added to planned analyses of efficacy data. Both measurements provide useful assessments of responses to study drug by the right heart. Neither hemodynamic measurement was included in the protocol defined endpoints.

The protocol states that the major protocol deviation “Did not receive all weekly infusions” is an exclusion criterion for Per-Protocol Set. This criterion is updated to “Missed more than one study drug infusion” due to the impact of the COVID-19 pandemic. Other major protocol deviations with minor changes are updated due to the same reason.

6 PROGRAMMING SPECIFICATIONS

Analyses will be performed using SAS® version 9.3 or higher. All available data will be presented in subject data listings which will be sorted by subject and visit date as applicable. Detailed Programming Specifications will be provided in a separate document.
